## C. Enrollment

### 1. Patient Population and Setting

The Johns Hopkins Hospital (JHH) NICU is a 45 bed NICU in a quaternary care center that admits approximately 700 neonates per year. The Johns Hopkins Bayview Medical Center (Bayview) NICU is a 25-bed, level III unit with approximately 375 admissions per year. Neonates admitted to the JHH and Bayview NICUs and their parents or legal guardians will be screened for eligibility. **We will define parents as the biologic mother and the father. In the event that one of the parents is not available or does not visit the child in the NICU, we will ask the available parent to identify a primary visitor of the child in the NICU. Only 2 parents or one parent and one primary visitor will be enrolled for each neonate. In the protocol below, parents will refer to either a parent or a designated primary visitor.**

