## **5. Screening**

The PI and/or a member of the research team will provide information regarding the study, answer any questions and obtain informed consent. The PI will be available in person or via telephone to answer any questions when a member of the research team is present for the consent. As part of the informed consent document, the subject will receive information on how to contact a study team member to discuss culture results or any noted treatments that may be related to *S. aureus*. Once consented, a member of the research team will assign a screening number (SN) to the subject. If the cultures are positive, the family unit will be enrolled and assigned a study identification number (SIN). This will be the primary mode of identification throughout the study. The SIN will identify the parent and the neonate (or neonates in the case of multiple gestations). The SIN will also identify both parents (if both consent to participate as both will be assigned to the treatment group). The SIN and/or SN will appear on the consent form, the data collection form, as well as all *S. aureus* cultures. If the cultures test negative, the family unit will not be randomized to treatment. However, parent participation in the study will not end. They will be asked to continue their participation in the study by completing a follow-up questionnaire approximately four weeks after their initial screening visit.

During the screening visit, a member of the research team will perform the necessary swabs to be sent for culture. The parent(s) who consent to undergo testing will be screened by obtaining a swab from the following anatomical sites: bilateral anterior nares, the throat, the groin/perineum, and the peri-anal area. A standardized check-list for obtaining and processing swabs will be used. For neonates transferred from an outside hospital or from home that did not have surveillance cultures obtained on admission, screening cultures will be performed by obtaining a swab from the following anatomical sites: bilateral anterior nares, umbilicus, groin, and peri-anal area.

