All swabs will receive a study number pre-printed on a label. The SN will not identify the patient's name, medical record number or other identifying information. The SN will be recorded on the informed consent documents and the surveillance swabs. Before sending the swabs, a member of the research team will take a brief "time-out" to reassess that all paperwork is completed, that swabs are appropriately labeled with SN, and that all consent forms and swabs contain the same SN.

Laboratory methods for determining whether a patient has *S. aureus* colonization are described below in Section 7.B. *S. aureus* colonization will be defined as a culture from any anatomic site that grows *S. aureus*.

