## 6. Allocation

**Randomization and masking:** This study has taken into consideration the guidelines for reporting of clinical trials as recommended by the CONSORT report to inform the study design. After recruitment and informed consent, parents will undergo pre-randomization screening. If both parents screen negative for *S. aureus* colonization, the neonate will be ineligible for the randomization and parents will be informed that they are not colonized at that time with *S. aureus*. If either parent screens positive for *S. aureus*, then both parents as a pair will be eligible for randomization to one of the two possible masked treatment arms. The neonate-parent "pair" will be the unit of randomization and each parent will be allocated to the same group if both consent. Because couples can re-expose each other after treatment (especially in households) we have chosen to treat both parents even if only one parent is colonized with *S. aureus*. To prevent potential feelings of guilt or one parent blaming another if only one parent is colonized, the parents will be told that one or both is colonized with *S. aureus* and they are eligible for randomization. Discordant parents will not be informed which is colonized and which is not colonized as we will treat both regardless.

Arm 1 will include assignment to masked intranasal mupirocin plus chlorhexidine gluconate cloths for topical antisepsis. Arm 2 will include assignment to masked placebo ointment and placebo cloths for skin antisepsis. Stratified permuted-block randomization will be performed using R statistical software to achieve balanced allocation of subjects within study site (Johns Hopkins Hospital vs. Bayview) and within strata of birth weight

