Adverse events, as defined in Section 8, will be reported overall and separately by treatment group. Comparisons across treatment groups will be made using Fisher's Exact tests.

In addition, a series of planned secondary analyses will be conducted including subgroup analyses for the primary outcome, baseline-covariate adjusted analyses for the primary and secondary outcomes, per-protocol (PP) analyses for the primary and secondary outcomes and evaluation of patterns of loss and reacquisition of *S. aureus* among the parents (both treated and control).

Planned subgroup analyses include repeating the analysis for the primary outcome within strata defined by i) neonates with MRSA vs. those with MSSA, ii) collection site of colonization for the parent/caregivers, categorized as nares alone (i.e. all cultured parent/caregivers colonized in the nares) vs. nares + other (i.e. at least one parent/caregiver colonized in the nares) vs. non-nares; iii) LGA (large for gestational age) vs. SGA (small for gestational age); and iv) birthweight (< 1500g vs.  $\geq 1500$ g). The subgroup analyses will be based on Cox proportional hazards models that include a main term for treatment, a main term for subgroup (binary indicator) and the interaction between treatment and subgroup. Confidence intervals and the hypothesis test for no interaction will be derived based on the bootstrap procedure defined above.

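### The parental carriage-site subgroup is labelled by body site but defined by counting nasal carriers, and has one binary term for three levels, so it cannot isolate the effect of added extranasal carriage

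*Combined protocol and SAP*

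**What the plan says.** Section 9.C plans four subgroup analyses of the primary outcome. Item ii classifies families by where the parents or caregivers are colonized: "nares alone (i.e. all cultured parent/caregivers colonized in the nares) vs. nares + other (i.e. at least one parent/caregiver colonized in the nares) vs. non-nares". The third group has no definition beyond its name. Two analyses are described for all four subgroups. One is "repeating the analysis for the primary outcome within strata defined by" the listed factors. The other is a Cox model with "a main term for treatment, a main term for subgroup (binary indicator) and the interaction between treatment and subgroup".

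Three other passages determine which families reach this subgroup:

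- Section 4.C.5 (Screening) has each consenting parent swabbed at four sites: "bilateral anterior nares, the throat, the groin/perineum, and the peri-anal area". Carriage at any one of them qualifies, because "colonization will be defined as a culture from any anatomic site that grows" *S. aureus*.
- Section 4.C.1 limits the family to two adults: "Only 2 parents or one parent and one primary visitor will be enrolled for each neonate".
- Section 4.C.6 (Allocation) randomizes couples in which only one is a carrier: "Because couples can re-expose each other after treatment (especially in households) we have chosen to treat both parents even if only one parent is colonized".

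**The concern.** The label and the rule measure different things. *Nares alone* and *nares + other* are statements about sites. The rules attached to them ask how many caregivers are nares-positive: all, or at least one. Neither looks at an extranasal swab, although three of the four screening sites are extranasal.

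The study regimen has a nasal part (ointment) and a skin part (cloths), and item ii is the only effect-modification analysis in Section 9.C by site of carriage. A reader of the results will take *nares alone* versus *nares + other* as a comparison of nose-only with multi-site carriage. Under the written rules, families with multi-site carriage sit in both groups. If culture-negative partners count under the first rule, nose-only families sit in both groups too. In that case the split depends partly on how many caregivers carry, so a difference between the groups could reflect the number of carriers rather than the site.

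The model adds a second gap. Three levels need two indicators, and the text does not say how they become one. The coding would have to be chosen later, which weakens the pre-specification.

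**Working it through.** **Step 1. List the possible families.** Inputs: one or two caregivers (4.C.1), carriage at any site qualifies (4.C.5), at least one carrier per family (4.C.6). Each caregiver is N (nares only), E (extranasal only), B (both) or neg. One caregiver gives 3 patterns. Two give 10 unordered pairs, less neg/neg, which is 9. The total is 12.

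**Step 2. Apply the rules.** Rule 1 is that all cultured caregivers are nares-positive. Rule 2 is that at least one is. The *Filed* column applies rule 1 first and rule 2 to the remainder, and counts a culture-negative caregiver as cultured.

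| Family | Rule 1 | Rule 2 | Filed | Sites positive in family |
|---|---|---|---|---|
| N | yes | yes | nares alone | nares |
| B | yes | yes | nares alone | **nares and other** |
| E | no | no | non-nares | other |
| N, neg | no | yes | nares + other | **nares** |
| B, neg | no | yes | nares + other | nares and other |
| E, neg | no | no | non-nares | other |
| N, N | yes | yes | nares alone | nares |
| N, B | yes | yes | nares alone | **nares and other** |
| B, B | yes | yes | nares alone | **nares and other** |
| N, E | no | yes | nares + other | nares and other |
| E, B | no | yes | nares + other | nares and other |
| E, E | no | no | non-nares | other |

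- Five patterns meet rule 1, and all five meet rule 2. The first group lies wholly inside the second. If rule 2 were applied first, the first group would be empty.
- Applied in order, the groups hold 5, 4 and 3 patterns. Four of the 12 contradict their label (bold): three in *nares alone* and one in *nares + other*.
- If *all cultured* means only culture-positive caregivers, both (N, neg) and (B, neg) move to *nares alone*. The first is then consistent with its label and the second is not. The groups hold 7, 2 and 3 patterns, and four of 12 still contradict the label.
- B, (N, B) and (B, B) are filed as *nares alone* under both readings.
- E, (E, neg) and (E, E) are *non-nares* under both readings.

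**Step 3. Compare model and categories.** Three levels need 3 − 1 = 2 indicators, 2 interaction terms and a 2-df test. Section 9.C specifies 1 indicator and 1 interaction term.

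**Step 4. What a corrected analysis could detect.** The plan gives no power figure for subgroups. Its primary figure reproduces with the Schoenfeld formula, 1:1 allocation, two-sided 5% and 80% power: 4(1.960 + 0.842)² / (ln 0.4)² = 37.39, and 37.39 × 1.02 = 38.14, matching the stated 38 events including interim inflation. The same variance gives, for a binary split with e₁ and e₂ events, SE of the difference in log HR = √(4/e₁ + 4/e₂). With 40 events in total, and an assumed HR of 0.4 in one group and 1.0 in the other:

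| Share of events in smaller group | SE | Ratio of HRs detectable with 80% power | Power |
|---|---|---|---|
| 10% | 1.054 | 19.2 | 13.8% |
| 20% | 0.791 | 9.2 | 21.2% |
| 30% | 0.690 | 6.9 | 26.4% |
| 50% | 0.632 | 5.9 | 30.5% |

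For the 2-df test, with HR 0.4, 0.4 and 1.0, the noncentrality is Σ(eᵢ/4)(bᵢ − b̄)², where bᵢ is the log HR and b̄ its event-weighted mean. It is 1.87 with events split in thirds (power about 21%) and 1.34 with a 40/40/20 split (power about 16%). The event shares and subgroup HRs are assumptions; the documents give none.

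**The case against.** The best defence has four parts.

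- *The rules form a hierarchy.* All, then at least one, then none reads naturally as a sequence and is exclusive when so applied. That largely answers the overlap, although the plan does not state the order. It does not answer the label problem, because the three patterns with universal nasal carriage plus another site still land in *nares alone*.
- *The rule governs and the label is just a poor name.* In that case nothing is misfiled, but the analysis compares numbers of nasal carriers and is reported under site names. If instead one adds *only* to the first rule, reads *cultured* as culture-positive, and applies the second rule to the remainder, the groups become those proposed under the fix. That may be what was meant, but it takes three insertions that the text does not make.
- *The binary indicator is shorthand.* The phrase covers four subgroups, and dummy variables for a three-level factor are routine. This is plausible, but the text does not say so.
- *Extranasal is itself a mixture.* It pools the throat with the groin and peri-anal sites, and the cloth areas listed in Section 4.B do not include the throat. This stands. Site-based groups answer the question in the labels, not a clean nose-versus-skin question.

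A reader might also infer that the subgroup can say nothing about non-nasal carriage. The documents do not support that. The non-nares group is exclusive on any reading, and the planned within-stratum analysis yields its hazard ratio without a subgroup indicator.

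**Conclusion.** The point holds in a limited form. As written, item ii cannot show whether extranasal carriage in addition to nasal carriage modifies the treatment effect. That conclusion rests on the wording alone: the rules do not use extranasal results. Any-nares versus non-nares remains estimable, although the plan does not name that contrast.

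The number of families affected is unknown. A reader might take the figure of about 30% carriage in healthy adults (Section 6.D) and infer that most families are misclassified, since 2 × 0.3 × 0.7 = 0.42 of 1 − 0.7² = 0.51 eligible couples would have exactly one carrier. That does not follow. It describes one-carrier couples, not misclassified ones. It assumes two cultured adults in every family and independence between them, whereas Section 4.C.6 itself expects couples to re-expose each other. It bears on the label only for nares-only carriers with a negative partner, and only if negative partners count as cultured. The documents do not give the nares-only fraction, so no misclassification rate can be calculated.

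The consequence is confined to one planned subgroup analysis. The primary analysis is unaffected. With about 40 events, even a corrected version has roughly 14% to 31% power under the assumptions shown, so it is exploratory either way.

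**What to change.** Before unmasking, replace item ii with exclusive family-level groups derived from the screening swabs of all cultured caregivers:

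1. Nares only: at least one nares-positive culture and no extranasal site positive in any cultured caregiver.
2. Nares plus extranasal: at least one nares-positive and at least one extranasal-positive culture in the family, whether in the same caregiver or different ones.
3. Extranasal only: at least one extranasal-positive culture and none from the nares.

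These place the 12 patterns once each (3, 6 and 3) and settle couples with one carrier. Name the screening swabs as the source, because under Table 1 the peri-anal site is not swabbed at the interim follow-up visits.

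Fit two indicators with a 2-df treatment-by-subgroup test, using the bootstrap already planned. Alternatively, keep a single binary term and pre-specify it as any extranasal carriage, yes or no. State that extranasal pools throat, groin and peri-anal sites, and that the analysis is exploratory.

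The cost is a few lines of SAP text and one derived variable. No new data are needed, and Section 9.C already provides for documenting changes in the analysis before database lock and unmasking.

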## **8. Data Collection and Data Monitoring**

Prior to any work being performed on this research proposal it will be submitted for review and approval by the Institutional Review Board at JHU. We will maintain a master list of patients with unique study identifiers. The master list will be maintained on a password protected computer or institutional network drive. Data will be entered into a database that will be stored on a secure server at the Johns Hopkins University. All research staff will be instructed as to how to maintain the highest ethical standards in protocol adherence and data collection. Standard backup procedures are in place at the institution to prevent catastrophic loss of data. Validity and accuracy checks will be put in place as data are entered into the database using preset field choices where applicable. Edits of the data will be performed routinely to look for missing data, outliers, unusual or inconsistent values. We will collect information on all neonates and parents enrolled in the study.

**For parents**, using standard questions that will be incorporated into the case report form, we will collect their date of birth, race, ethnicity, gender, educational level, underlying medical conditions (especially skin diseases that predispose to *S. aureus* colonization), current medications, exposure to recent antibiotics, recent healthcare exposures, other household members, past use of mupirocin, and dates of, and treatments for any prior *S. aureus* infections.

**For neonates**, we will collect basic demographic information on all patients, including chronologic age (date of birth), birth weight, mode of delivery, gestational age, race, ethnicity, gender, antimicrobials (antibiotics, antifungals, antivirals) administered, other interventional or clinical medicines that may impact *S. aureus* colonization, presence of central venous catheter, respiratory support, feeding method (breastfeeding, orogastric tube, nasogastric tube), dates of NICU admission and discharge, primary reason for admission (primary condition), where neonate was admitted from (home, other hospital, inborn), procedures, number of trips to the operating room or radiology, on NP or resident service, number of consulting teams, APGAR scores, practice and timing of kangaroo care, days in isolette vs. open crib or bed, dates and results of all *S. aureus* surveillance cultures and other cultures sent during routine clinical care.

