## **9. Statistical Analysis Plan**

### **A. Sample size and power estimates:**

The primary outcome will be time to concordant *S. aureus*-colonization. Time to concordant *S. aureus* colonization will be expressed using an indicator variable for concordant colonization and time to concordant colonization. The a priori assumed

control group concordant colonization rate is 10% and power calculations are based on the unadjusted Cox proportional hazards model where the primary covariate is the treatment group indicator. In time to event analyses, power is driven by the number of events; i.e. number of concordant colonizations. Given our assumed control group concordant colonization rate of 10%, 38 events are required to detect a 60 percent reduction in the hazard of concordant colonization (Hazard Ratio: HR 0.4) in the intervention group with 80% power and Type I error rate of 5%. The 38 events includes a roughly 2% inflation for pre-planned interim analyses (see Section 9.B). Given that we expect 5% of the parent-neonate pairs will be non-singleton births, we increased the number of required events to 40 to account for the possible clustering of concordant colonization among non-singleton neonates. Some neonates may test positive at baseline for *S. aureus* after randomization and will not be eligible for the analysis of the primary outcome. Similarly, if one neonate from a multiple gestation birth is positive for *S. aureus* at baseline and another neonate is not, then the negative infant will be eligible. Eligible parent-neonate pairs will be assigned to either treatment or control as a unit until 40 events are confirmed. Prior to the start of the study, given our *a priori* assumption of a 10% concordant colonization rate in the control group and a HR of 0.40, we anticipated recruiting 400 parent-neonate pairs to achieve the required 40 concordant colonizations. With 400 parent-neonate pairs, we have roughly 80% power to detect an absolute risk difference of at least 7% for the secondary analysis of the indicator of concordant colonization within 90 days after randomization.

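### The size-for-gestational-age subgroup names only the two extremes, so appropriately grown neonates have no stratum in that one model

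*Combined protocol and SAP*

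**What the plan says.** Section 9.C (Statistical analysis plan) introduces the subgroups with "Planned subgroup analyses include repeating the analysis for the primary outcome within strata defined by" and lists four items. The third is "LGA (large for gestational age) vs. SGA (small for gestational age". Each subgroup is to be fitted by a Cox model with "a main term for treatment, a main term for subgroup (binary indicator) and the interaction between treatment and subgroup". Confidence intervals and the interaction test come from the bootstrap used for the primary analysis.

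No section mentions infants of appropriate size for gestational age, gives a percentile or growth reference for SGA or LGA, or says what happens to a neonate who is neither. The fourth subgroup in the same sentence, birth weight split at 1500 g, does cover every neonate.

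The data needed to classify size are already planned. Section 8 (Data Collection and Data Monitoring) lists "chronologic age (date of birth), birth weight, mode of delivery, gestational age, race, ethnicity, gender" among the neonatal variables. Section 9.A sets the final target at 40 primary events.

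**The concern.** Large and small for gestational age are the outer categories of one scale, and the category between them is missing. With only two named strata, an AGA neonate has no value for the subgroup variable. An analyst who follows the text fits the model to the tails and omits the middle. An analyst who does not must decide where AGA infants go, and the plan does not settle that choice in advance.

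The stake is the usefulness of this one analysis. As written, its hazard ratios and interaction test use only part of the events and contrast two extremes. They would not show whether the effect in SGA infants differs from that in all other infants.

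**Working it through.** The exclusion is a matter of text, and arithmetic only sizes it.

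**The plan's own figure.** Section 9.A says "38 events are required to detect a 60 percent reduction in the hazard of concordant colonization", "with 80% power and Type I error rate of 5"%. Schoenfeld's formula with 1:1 allocation and a two-sided test gives 4 × (1.960 + 0.842)² / (ln 0.40)² = 37.39 events. With the stated inflation of roughly 2% for interim looks this is 38.14, so the 38 reproduces. Section 9.A then raises the target to 40 for multiple births.

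**Assumptions for the subgroup.** The LGA and SGA shares are not in the documents. I assume that:
- LGA plus SGA is 20% to 40% of neonates, so AGA is 60% to 80%;
- events fall in proportion to those shares;
- the tail events divide equally between LGA and SGA.

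**Events retained as written.** 40 × 0.20 = 8, and 40 × 0.40 = 16.

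**Precision of the interaction.** With events d1 and d2 in two strata and equal division between arms, SE of the log ratio of hazard ratios = √(4/d1 + 4/d2), and the 95% confidence interval factor = exp(1.96 × SE).

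| LGA + SGA share | Coding | Events d1, d2 | SE | Factor either way |
|---|---|---|---|---|
| 20% | LGA vs SGA | 4, 4 | 1.41 | 16 |
| 20% | SGA vs not SGA | 4, 36 | 1.05 | 7.9 |
| 40% | LGA vs SGA | 8, 8 | 1.00 | 7.1 |
| 40% | SGA vs not SGA | 8, 32 | 0.79 | 4.7 |

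The rows must be compared within the same assumed share: 16 falls to 7.9, or 7.1 falls to 4.7.

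**Power in the retained set.** Power for a hazard ratio of 0.40 = Φ(0.916 × √d / 2 − 1.96), ignoring interim looks. It is 25% with 8 events and 45% with 16, against 83% with all 40.

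**Sparse cells.** The table is somewhat favourable, because at a hazard ratio of 0.40 the treated arm has about 0.4/1.4 = 29% of events. With 4 events in a stratum, the chance that one arm has none is 0.286⁴ + 0.714⁴ = 27%, and the chance that this happens in at least one of two such strata is 1 − 0.733² = 46%. The interaction then has no finite estimate. With 36 events on the other side, only the SGA stratum carries this risk, so the fix lowers it to about 27% but does not remove it.

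**The case against.** **Scope.** A reader might infer that most neonates drop out of the trial's analysis. The documents do not support that. Every neonate negative at baseline stays in the modified intention-to-treat primary analysis, in the birth-weight subgroup and in the covariate-adjusted analysis, which uses continuous birth weight. The gap is confined to item iii.

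**The binary indicator.** A reader might also take "a main term for subgroup (binary indicator) and the interaction between treatment and subgroup" to commit the plan to a two-level model. But item ii, the parental colonization site, has three levels under the same sentence, so the phrase is loose and a third AGA level is not ruled out by it. This stands. The exclusion follows from the two strata that item iii names, not from the word binary.

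**A looser meaning.** The authors may have meant not SGA when they wrote LGA. Both terms are spelled out and nothing indicates this. If it was the intent, the wording still needs the same correction.

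**Size.** No share is documented, so all the figures above are conditional. That AGA infants are the majority rests on the usual meaning of the terms and holds only if LGA and SGA together are below 50%.

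**The fix does not rescue the test.** Correct: a factor of 7.9 or 4.7 either way is still too wide to support a conclusion. A reader might set 16 beside 4.7 as the gain, but that changes the assumed share as well as the coding.

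**Conclusion.** The point holds for one secondary subgroup analysis. As written, item iii gives AGA neonates no stratum and excludes them from that model. Under the assumed 20% to 40% share for the two tails, it keeps about 8 to 16 of the 40 events. Coding SGA against everyone else roughly halves the confidence interval factor at the lower share (16 to 7.9) and cuts it by about a third at the higher share (7.1 to 4.7).

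The exclusion itself needs no assumption about shares; only its size does. The interaction result would be exploratory under either coding. The primary estimate, the event target and the stopping boundaries are untouched. Severity is low to moderate.

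**What to change.** Replace item iii with SGA versus not SGA, stating that the second group holds AGA and LGA infants together. Name the percentile cut-off and the growth reference, without which neither coding can be run. Derive the class from "chronologic age (date of birth), birth weight, mode of delivery, gestational age" and gender, all already collected, so that every neonate in the modified intention-to-treat set enters the model. Label the result exploratory.

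A three-level factor or a continuous weight-for-age z-score would also keep every neonate, but each would require the model sentence to be reworded.

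The cost is a few lines of SAP text. Section 9.C already provides for analysis changes to be recorded before the database is locked and assignments are unmasked, and this change should be made by then.
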